2.7 Safety of TUTT and TUTT-PT

A primary goal is to test the safety of universal TPT with TUTT. To maximize safety in terms of immediate receipt of appropriate anti-TB therapy, each clinic, irrespective of arm, will be supported by a PHRU study team tracer. Any participant who tests positive for TB will be immediately contacted by the tracer telephonically. Those who cannot be reached via telephone will be visited at the household by the tracer to alert the participant of their TB test result and facilitate return to the clinic for switch from TPT to anti-TB treatment (or to initiate anti-TB treatment if not on TPT). All participants who test positive for TB will have two additional spot sputum specimens collected on the date of anti-TB treatment initiation. The first specimen will be used as per routine care. The second specimen will be sent for study-specific culture and drug-susceptibility testing.

Participants who test positive for TB will be referred to clinic staff for termination of TPT and initiation of anti-TB treatment. Those with trace results on Xpert Ultra will be managed as per routine care. No further interaction between the study nurse and the participant will take place thereafter.

All participants who are prescribed TPT will be contacted 1 month after TPT initiation by the PHRU study team tracer to check for side effects and/or signs of any TPT-related adverse events. Participants who report potential side effects or adverse events will be referred to clinic staff for ongoing management. The Principal Investigator will promptly report to Human Research Ethics Committee any changes in research activity and all unanticipated problems involving risk to human subjects or others.

2.8 Outcomes and analysis

The primary outcomes are the proportion of PLHIV who initiate TPT within 7 days of ART start and the median time to TB treatment initiation for those who test positive for TB. ART initiators include clients who are ART naïve and those re-initiating ART after a lapse in treatment. Secondary outcomes are included in the table below. TB test results and TPT initiation will be ascertained from study source documents and all available data sources in the clinics, including but not limited to paper files, electronic files (Tier.NET and DHIS2), clinic registers, pharmacy records, and lab test results. Analytic approaches are described in the table below.

Table 1. Outcomes & analysis approach

	Outcomes	Data source	Statistical Test
Primary	Proportion of PLHIV who initiate TPT within 7 days of ART (re-)initiation	Paper files, electronic files, clinic registers, pharmacy records, lab test results	Chi-square
Primary	Proportion of PLHIV who initiate TPT and have a subsequent positive TB test result	Paper files, electronic files, clinic registers, pharmacy records, lab test results	Chi-square
Primary	Healthcare provider experiences with universal TB testing and TPT provision	In-depth interviews	N/A
Primary	Median time to TB treatment initiation for those who test positive for TB	Paper files, electronic files, clinic registers, pharmacy records, lab test results	Kaplan-Meier
Secondary	Proportion of PLHIV evaluated for ART (re-)initiation tested for TB within 7 days of ART start, stratified by TB symptom status	Paper files, electronic files, clinic registers, pharmacy records, lab test results	Chi-square
Secondary	Prevalence of active TB disease among PLHIV evaluated for ART (re-)initiation, stratified by symptom status	Paper files, electronic files, clinic registers, pharmacy records, lab test results	Chi-square
Secondary	Median time from ART initiation to TPT initiation	Paper files, electronic files, clinic registers, pharmacy records, lab test results	Kaplan-Meier
Secondary	Proportion of PLHIV diagnosed with TB who remain on TPT for 7 days or longer	Paper files, electronic files, clinic registers, pharmacy records, lab test results	Chi-square
Secondary	Prevalence of TB drug resistance at TB treatment initiation, stratified by TPT use at the time of TB diagnosis	Paper files, electronic files, clinic registers, pharmacy records, lab test results	Descriptive proportions
Secondary	TB incidence rate within 6 months of ART initiation	Paper files, electronic files, clinic registers, pharmacy records, lab test results	Descriptive proportions

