2.9 Sample size justification

We hypothesize that TPT prescribing will be 65% in routine TUTT implementation and 80% in TUTT-PT implementation. Thus, we will enrol 200 PLHIV in TUTT clinics and 200 PLHIV in clinics where they will receive TUTT-PT (450 total) in order to detect this difference with 80% power at a 5% level of significance while accounting for clustering by clinic (a design effect of approximately 1.3). A sample size of 450 will also enable us to identify an estimated 20 new ART clients diagnosed with TB (assuming prevalence of 5%) in order to evaluate time to TB treatment initiation. In addition, throughout study implementation, we will conduct ongoing monitoring of intervention safety, defined as the number of participants diagnosed with TB who remain on TPT after diagnosis by study arm.

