7.2 Risks and benefits

- The primary goal of this study is to improve prescribing of TPT. Due to the nature of the intervention in which participants will be prescribed ART and TPT prior to receipt of their TB test result, irrespective of the presence or absence of TB symptoms, the risk exists that participants with active TB disease will be on INH monotherapy for a short duration of time. However, we intend to trace participants and switch them to anti-TB treatment within 72 hours of sputum collection; thus, participants later determined to have active TB disease should not be on INH monotherapy for more than 7 days (accounting for the weekend) prior to anti-TB treatment initiation. Additionally, all participants, irrespective of study arm, will provide an additional specimen for culture and drug susceptibility testing. This will enable the study team

to immediately refer any participant with evidence of drug resistance to a doctor for further evaluation and drug-resistant TB treatment initiation, if necessary.

- Among participants there is a risk of inadvertent disclosure of HIV status. This risk will be addressed through training of study staff and secure storage of all study documents.
- Among health care workers recruited for in depth interviews there is a risk of inadvertent release of comments about care proficiency. All documents and data will be confidential and securely stored. No individual level results will be provided to other health care workers, clinic management, or Department of Health personnel.

7.3 No excessive inducements for participation.

There will be no excessive inducements for the participants, except for consenting and completion of questionnaires/interviews.

7.4 The information is presented in language that is understandable to the subject population.

The Participant Information Sheet (PIS) and other study related communication is at the participant level. Additionally, the PIS will be translated into the appropriate common local languages (eg. Setswana, Sesotho and Isixhosa) spoken in North West province.

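### The primary safety measure is a median in about 10 TB cases per arm, which hides delays beyond the 7-day limit in Section 7.2, and the monitoring count omits time on TPT before diagnosis

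*Combined protocol and SAP*

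**What the plan says.** - **Primary safety measure.** Section 1.2, objective 3, estimates the safety of each approach from the median time to TB treatment among those testing positive. Section 2.8 lists the "median time to TB treatment initiation for those who test positive for TB" as primary. Table 1 gives Kaplan-Meier as the method. It names no confidence interval, no estimate at day 7, no time origin, and no handling of deaths or losses before treatment.
- **Secondary 7-day outcome.** Table 1 also lists "Proportion of PLHIV diagnosed with TB who remain on TPT for 7 days or longer", analysed by chi-square. It does not say from which date the seven days run.
- **Monitoring during the study.** Section 2.9 defines intervention safety as "the number of participants diagnosed with TB who remain on TPT after diagnosis by study arm". No threshold is attached. Section 7.6 states that there is no data safety and monitoring board.
- **The risk as described.** Section 7.2 says that participants later found to have TB "should not be on INH monotherapy for more than 7 days (accounting for the weekend) prior to anti-TB treatment initiation".
- **Number of cases.** Section 2.9: "A sample size of 450 will also enable us to identify an estimated 20 new ART clients diagnosed with TB (assuming prevalence of 5" per cent). It gives no precision for any safety outcome.

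**The concern.** Section 7.2 limits how long any one participant with undiagnosed TB stays on preventive therapy alone. That is a statement about the slowest patients, whereas a median describes the middle one. An arm could report a short median while a substantial minority of its TB cases exceeded the limit.

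The two other measures do not clearly close the gap. The secondary row could run from TPT start, which is the exposure in Section 7.2, or from diagnosis, which leaves out the time spent waiting for the result. Section 2.9 speaks of remaining on TPT after diagnosis, so the second reading is plausible. The monitoring count uses that second reading explicitly. It is therefore blind to slow return of results, one of the two steps (return of the result, then tracing) on which the 72-hour target in Section 6 depends. With no monitoring board, this count is the planned in-study check on TPT exposure in TB cases.

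**Working it through.** **1. The plan's case count.** Section 2.9 gives 200 participants per arm and 5% prevalence.
- 400 × 0.05 = 20, which reproduces the plan's figure, or 10 per arm.
- The same sentence attaches the 20 to a total of 450, but 450 × 0.05 = 22.5 (11.25 per arm if split evenly). The two totals should be reconciled; the difference does not affect this point.
- The summary's background gives 5–8% testing positive. At 8%, 200 × 0.08 = 16 per arm.
- Section 1.1.2 cites 13–19% in ART-naïve people tested regardless of symptoms, giving 200 × 0.13 = 26 to 200 × 0.19 = 38 per arm. This is the upper end of what the documents could support and is not the plan's assumption.

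**2. TB cases exposed to TPT.** Section 2.9: "We hypothesize that TPT prescribing will be 65% in routine TUTT implementation and 80% in TUTT-PT implementation". If uptake is the same in TB cases as in everyone else (an assumption), then of 10 cases per arm, 10 × 0.80 = 8 are exposed in the TUTT-PT arm and 10 × 0.65 = 6.5 in the standard arm.

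**3. What the median can hide.** Order 10 times to treatment and assume no censoring before the middle of the distribution. The median lies at the 5th value, or between the 5th and 6th, depending on convention. On either convention, values 7 to 10 can be any length, or never occur, without changing it. So 4 of 10 (40%) could exceed 7 days with a median at or below 7 days. An order-statistic interval for the median of 10 runs from the 2nd to the 9th value (97.9% coverage), so the median itself is also poorly determined.

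**4. What the monitoring count can hide.** Take diagnosis to mean the positive result. As an illustration, a participant starts TPT on day 0, the result returns on day 14, and TPT stops that day.
- Days on TPT after diagnosis: 14 − 14 = 0, so the participant is not counted.
- Days on TPT before TB treatment: at least 14, twice the 7 days in Section 7.2.

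**5. Precision of a 7-day proportion.** With zero events in n cases, the exact two-sided 95% upper limit is 1 − 0.025^(1/n).

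| Cases in the arm | Basis | Upper limit with 0 events |
|---|---|---|
| 8 | TPT-exposed, TUTT-PT arm, 5% | 36.9% |
| 10 | all TB cases, 5% | 30.8% |
| 16 | all TB cases, 8% | 20.6% |
| 20 | both arms pooled, 5% | 16.8% |

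An upper limit below 20% with no events needs 17 cases in the arm, and below 10% needs 36. Conversely, a true risk of 10% gives no events in 10 cases with probability 0.9^10 = 35%, and a true risk of 20% does so with probability 0.8^10 = 11%.

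**The case against.** **The plan already measures the 7-day risk.** Table 1 has the secondary row, and a Kaplan-Meier curve would show the proportion untreated at day 7 if it were read there. This stands against any claim that the plan cannot show the risk. What remains is that the row has no stated origin or interval, and that the plan commits to reporting the median rather than a day-7 estimate.

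**A reader might infer that chi-square on such small numbers gives misleading p-values and should give way to Fisher's exact test.** The figures do not support this. By exact enumeration, the type I error of the uncorrected chi-square test is at most 4.2% at 10 versus 10 and at most 5.0% at 200 versus 200, over the low risks relevant here. Fisher's test has a type I error of at most 1.3% at 10 versus 10. For 0% versus 30%, its power is 15% against 35% for chi-square. In a safety comparison, the switch would make harm harder to detect. Nor is the outcome of TPT followed by a positive test confined to 10 patients: read over all enrolled, its denominator is about 200 per arm, with roughly 8 and 6.5 expected events under the assumptions above.

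**A reader might also infer that all safety evidence rests on the TB cases.** It does not. Section 2.7 provides a call at 1 month to everyone prescribed TPT. That call looks for side effects and adverse events, however, and does not measure time on TPT with undiagnosed TB.

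**The study is a pilot that says its inferences are limited (Section 5), and its objective is to estimate safety.** This is fair, and no power calculation for safety is being asked for. It is a reason to state the precision of the estimate.

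**The four late patients must be the slowest ones.** This is correct. If patients who would have started early fail to start, the median moves. Because the plan gives no censoring rule, the effect of early deaths on the Kaplan-Meier median is also undetermined. It should not be assumed that deaths will be censored.

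**Conclusion.** The point holds as a matter of definition and reporting. At the plan's own figures, the primary safety measure could stay at or below 7 days while 4 of 10 TB cases in an arm exceed that limit. The monitoring count would not register a participant whose whole exposure fell before the result. The secondary row partly covers the risk, but its start date is undefined and its cut-off (seven days or longer) does not match Section 7.2 (more than 7 days). Even a perfect result would leave an upper limit of 30.8% (0 of 10) or 36.9% (0 of 8), and the plan does not say so.

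These figures assume 5% prevalence, an even split of cases between arms, and equal TPT uptake in TB cases. At 8% the limit for all TB cases in an arm is 20.6%. Only near the top of the 13–19% range would a zero count bring it below 10%. The monitoring point assumes that diagnosis means the positive result. No fault is found with the choice of chi-square.

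**What to change.** 1. **Use one exposure definition.** For TB-positive participants, define time on TPT as days from TPT start to TPT stop or TB treatment start, whichever comes first. Use it for the 7-day row in Table 1 and for the monitoring count in Section 2.9. Reconcile the cut-off in that row with the one in Section 7.2; which is right is for the investigators to settle.
2. **Report the tail beside the median.** Keep the Kaplan-Meier median and state its time origin. Add, by arm and each with an exact 95% interval: (a) the proportion of all TB-positive participants who started TB treatment within 7 days of sputum collection, with deaths and losses before treatment counted as not started; and (b) the proportion of TPT-exposed TB cases beyond the 7-day limit. The first covers everyone who tests positive. The second matches the exposure in Section 7.2.
3. **State the expected precision in Section 2.9**, for example the upper limits for 0 of 10 and 0 of 8, and note that these intervals ignore clustering by clinic.

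No extra participants or visits are needed. The costs are wide intervals reported openly, some additional date abstraction, and ethics approval of an amendment. Section 4.1 lists the purpose of each form but not its fields, so confirm that the date of the first sputum specimen and the TPT stop date are captured. The sputum recorded at the TB follow-up visit is collected after the positive result and is not the diagnostic specimen.

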1.2 Study Objectives

The overarching goal of this study is to pilot universal TB testing combined with universal TB preventive treatment initiation among people living with HIV initiating ART in South Africa; we will evaluate the feasibility, infer effectiveness and assess possible adverse events associated with this strategy. We will utilize a mixed-methods design comprising of a non-randomized pilot evaluation and in-depth interviews to achieve our study objectives.

The primary objectives are:

1. To compare the proportion of PLHIV who initiate TPT within 7 days of ART initiation based on same day TPT or not.
2. To compare the proportion of PLHIV who initiate TPT and have a subsequent positive TB test result based on same day TPT or not.
3. To estimate the safety of each TPT initiation approach based on the median time to TB treatment initiation among those who test positive for TB based on same day TPT or not.
4. To understand health care provider experiences with implementation of universal TB testing and TPT provision for PLHIV initiating or re-initiating ART

The secondary objectives are:

1. To estimate the proportion of PLHIV evaluated for ART initiation who are tested for TB within 7 days of ART initiation, stratified by symptom status.
2. To determine the prevalence of active TB disease among PLHIV evaluated for ART initiation, stratified by symptom status.
3. To estimate the median time from ART initiation to TPT initiation
4. To determine the proportion of PLHIV diagnosed with TB who remain on TPT for 7 days or longer.
5. To estimate the prevalence of TB drug resistance at TB treatment initiation, stratified by TPT use at the time of TB diagnosis.
6. To estimate the incidence rate of new TB diagnoses within 6 months of ART initiation

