2.5 TUTT-PT (intervention) arm

In the TUTT-PT arm, newly initiating or re-initiating ART clients will be referred by clinic staff after ART initiation to the PHRU study nurse for eligibility screening and enrolment. All TUTT-PT arm participants who provide written informed consent will have sputum collected for TB testing (if sputum was not already collected by the clinic staff) and will receive a clinical evaluation for the presence of TB symptoms (cough, fever, weight loss, night sweats) and serious contraindications for TPT initiation (known liver disease, high alcohol intake (men: >5 drinks/day or >15 drinks/week; women: >4 drinks/day or >8 drinks/week), or strong clinical suspicion of TB disease as evidenced by severity of symptoms, including haemoptysis, or Karnofsky score ≤ 50). PLHIV for whom the study nurse does not have a strong clinical suspicion of TB nor evidence of serious TPT contraindications will be referred to clinic staff for TPT initiation, irrespective of the presence or absence of TB symptoms.

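### Deaths are recorded in both arms but no planned outcome reports them by arm, and plain Kaplan-Meier for time to TB treatment would by default censor untreated deaths

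*Combined protocol and SAP*

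**What the plan says.** Section 2.7 states: "A primary goal is to test the safety of universal TPT with TUTT". The overarching goal in section 1.2 includes a commitment to "assess possible adverse events associated with this strategy". Primary objective 3 turns safety into one quantity: "To estimate the safety of each TPT initiation approach based on the median time to TB treatment initiation", among those who test positive.

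Section 2.8 carries this forward as a primary outcome, the "median time to TB treatment initiation for those who test positive for TB". Table 1 gives its whole analysis as Kaplan-Meier. It states no time origin, censoring rule, treatment of death or between-arm test.

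Death appears as a data item in section 4.1, Table 2: PC001 documents completion, withdrawal and death, in both arms, as needed and at about 3 months. It does not appear in the four primary or six secondary objectives, in any row of Table 1, or in the ongoing monitoring of section 2.9, which counts participants with TB who stay on TPT after diagnosis. Section 7.6 says there is no data safety and monitoring board.

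**The concern.** The study asks whether starting TPT before the TB result is known is safe. A report could follow this plan completely and never show how many participants died in each arm. Whether and how to show deaths would then be decided after the data had been seen.

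The second issue is how the primary safety outcome handles death. A TB-positive participant who dies before treatment can never start it. Standard Kaplan-Meier censors that person, which treats them as still able to start. The death then does not count against the arm, and the estimated proportion treated can only be equal to or higher than the true one. Other things equal, the arm with more untreated deaths looks faster to treat, which this plan reads as safer.

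**Working it through.** **1. Number of TB-positive participants.** Section 2.9 expects 20 at 5% prevalence. 0.05 × 400 = 20, which reproduces the plan's figure from 200 per arm. With the stated total of 450, 0.05 × 450 = 22.5. That is about 10 to 11 per arm.

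**2. Direction of the bias.** With death as a competing event, the cumulative incidence keeps untreated deaths in the denominator. One minus the Kaplan-Meier estimate, with deaths censored, is never below it. The Kaplan-Meier median is therefore never later than the competing-event median.

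**3. One untreated death, effect on the median** (median taken as the first time the curve reaches 50%).
- n=10: cumulative incidence reaches 5/10 at the fifth treatment start. In the most extreme case, where the death precedes every treatment start, Kaplan-Meier is 4/9 = 44% at the fourth start. Both medians are the fifth start, so the shift is 0.
- n=11: cumulative incidence is 5/11 = 45% at the fifth start and 6/11 = 55% at the sixth, so its median is the sixth. If the death comes first, Kaplan-Meier is 5/10 = 50% at the fifth start, so its median is one treatment start earlier.

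**4. Illustration at n=10, assumed times.** Nine are treated on days 2 to 10 and one dies on day 3.

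| | Kaplan-Meier | Cumulative incidence |
|---|---|---|
| Treated by day 6 | 54% | 50% |
| Treated by day 7 | 66% | 60% |
| Treated by day 10 | 100% | 90% |
| Median | day 6 | day 6 |

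**5. Simulation, one death, assumed times.** I used 4,000 arms per setting, lognormal treatment times (median 3, 5 or 7 days; log-scale SD 0.6 or 1.0) and death uniform on days 0 to 7. The mean shift in the median was 0 in all six settings at n=10. At n=11 it was about 0.1 to 0.5 day, against a sampling SD of the median of about 0.8 to 3.4 days. The shift was below the SD in every setting.

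**6. How likely is such a death?** The plan gives no rate. At an assumed 0.5% to 5% risk of death before treatment, the chance of at least one among 20 cases is 1 − 0.995^20 = 10% to 1 − 0.95^20 = 64%.

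**7. All-cause deaths.** At an assumed 0.5% to 3% risk to 3 months, 200 × 0.005 = 1 to 200 × 0.03 = 6 deaths are expected per arm. The chance of at least one in an arm is 1 − 0.995^200 = 63% to 1 − 0.97^200 = 99.8%.

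**8. Precision of a mortality row.** Exact 95% intervals: 4/200 gives 0.5% to 5.0%; 1/10 TB-positives gives 0.3% to 44.5%. For 6/200 against 2/200 the difference is 2.0% (Newcombe interval −1.0% to 5.5%). A rough allowance for five clinics takes SE = √(0.03 × 0.97/200 + 0.01 × 0.99/200) = 1.4%. Multiplying by √1.3 gives 1.6%, and with t on 3 df (3.18) the interval is about −3% to 7%, before any confounding.

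**The case against.** The strongest reply is that the plan targets the specific hazard, TPT given during undiagnosed TB. It does so through time to treatment, TPT followed by a positive test, 7 or more days on TPT, drug resistance and the by-arm monitoring count. Deaths are already collected prospectively in both arms, so a count can be reported without any design change. The planned quantity is a median, which hardly moves. Section 6 aims to return TB-positive participants to the clinic within 72 hours of sputum collection, so deaths before treatment should be few. Section 5 already says that inference is limited. All of this stands, and it lowers the severity. It does not answer the main point, because none of those outcomes counts deaths and nothing commits the report to showing them. Ethics-committee reporting of "all unanticipated problems involving risk to human subjects or others" handles single events and is not a comparison by arm.

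A reader might also infer that deaths go undetected in participants not given TPT, because of this arrangement: "All participants who are prescribed TPT will be contacted 1 month after TPT initiation by the PHRU study team tracer". The documents do not support that. The call is a check for TPT side effects, so restricting it to people on TPT is reasonable. PC001 records deaths in both arms, and section 2.7 has TB-positive participants phoned, or visited if unreached, whether or not they are on TPT. The gap is in the analysis and reporting of deaths.

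**Conclusion.** The point holds, at minor severity. Deaths are recorded but no planned outcome reports them by arm, and the primary safety outcome has no rule for death before treatment.

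Three stronger readings are not supported:
- That the plan says untreated deaths will be censored. It is silent, and censoring is only what the named method does by default.
- That the reported median is seriously biased. With one untreated death the shift is 0 at n=10 and about 0.1 to 0.5 day at n=11. Clearly larger distortion needs two or more such deaths among about 10 cases. At the assumed 0.5% to 5% risk, the chance of that is 0.1% to 8.6%. The 100% against 90% contrast concerns a proportion that the plan does not propose to report.
- That a mortality row would establish or exclude a difference between arms. Even 6 against 2 deaths leaves an interval spanning zero, and the clinics are five and not randomised.

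Treatment times and death risks are assumptions throughout. The size of the median shift also depends on the convention for reading a median off a step curve.

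**What to change.** 1. Add one descriptive row to Table 1, drawn from PC001: all-cause deaths by arm to about 3 months, among all participants and among TB-positives, with exact 95% intervals. State that the intervals ignore clustering by clinic and confounding and do not support a formal comparison.
2. Replace Kaplan-Meier for time to TB treatment with cumulative incidence by arm, starting at sputum collection (the origin that section 6 uses for its 72-hour target in both arms). Treat death before treatment as a competing event. Read the median from that curve and also give the proportion treated by day 7. Day 7 echoes the limit on INH monotherapy in section 7.2. For standard-arm participants not on TPT it is simply a common time point.
3. Check that PC001 captures the date of death, and add the field if it does not.

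The cost is a change of wording in Table 1, a few lines of code and possibly one form field, with no extra visits or participants. The downside is that the time-to-treatment figures may look slightly less favourable and the mortality row will be imprecise.
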